This is a prospective, randomized, double-blinded, placebo-controlled clinical trial on lidocaine infusion for pain control and opioid consumption in patients undergoing either robotic-assisted laparoscopic prostatectomy or robotic-assisted laparoscopic partial nephrectomy at University of Missouri Hospital. Patients will be randomized in a 1:1 fashion and stratified by the type of surgery to receive a perioperative intravenous 0.8% lidocaine infusion at 1 mg/kg/h if $<$ age 65 and 0.5 mg/kg/h if \geq age 65 or an equal volume and rate of normal saline as a placebo. The infusion will be started 15 minutes after endotracheal intubation and continue for 24 hours.

After obtaining written consent, subjects will be randomized to receive lidocaine or normal saline. The anesthesiologist, surgeon, nurses, research staff, and patient will be blinded to the intervention. Masked infusion bags of 0.8% lidocaine or normal saline will be prepared by the investigational pharmacy at University of Missouri Hospital. To avoid any compromise in the blinding process, the investigational pharmacist will enter "Study Medication" in the medical record.

Perioperative care, surgery and anesthesia, for all subjects will be per standard hospital protocol.

In short:

Upon arrival to the operating room, patients will be placed supine on the operating table and intravenous (IV) lines connected to allow initiation of IV lidocaine or saline following anesthetic induction. IV antibiotics will be utilized if clinical necessary based on the discretion of the anesthesiologist and attending surgeon. Standard perioperative monitoring including a

continuous electrocardiogram, pulse oximetry, urine output, non-invasive arterial pressure measurement, end-tidal CO₂ and temperature will be utilized. Intravenous fluid use during surgery will be provided by the anesthesiology team as clinically indicated. Anesthesia will be standardized. Induction will be with lidocaine 1.5 mg/kg, fentanyl 1 mcg/kg, propofol 1.5 to 2 mg/kg, and rocuronium 0.6 mg/kg. Patient will then be prepared and draped in sterile fashion. Timeout will be performed.

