The technique of surgery will have been determined to be robotic assisted laparoscopy based on the discretion of the surgeon and patient. None of the techniques utilized in the study are considered experimental and all are considered standard therapeutic options for the patient with either a prostate cancer or a renal mass concerning for cancer amenable to prostatectomy or partial nephrectomy, respectively. Since patients will be undergoing the same approach, impact from physiologic differences between the 2 approaches are expected to be equally distributed between the 2 arms and the randomization will be additionally stratified by the type of the surgery. Patient medications will be recorded from the home medications list and managed perioperatively per institutional standards.

The operating team will consist of surgeons on faculty at University of Missouri Department of Surgery-Urology Division. The procedures are performed under standardized general anesthesia with standard intraoperative vital sign monitoring.

EVALUATION DURING TREATMENT/INTERVENTION

This protocol does not require any additional evaluations after the subject is admitted for surgery other than those routinely part of clinical care for a patient undergoing robot assisted laparoscopic prostatectomy or robot assisted laparoscopic partial nephrectomy other than inquiring for subjects' satisfaction on postop day one and monitoring for signs of lidocaine toxicity during inpatient hospitalization. Signs of possible lidocaine toxicity include the presence of perioral paresthesia, metallic taste, tinnitus, confusion, agitation, muscle spasms, and seizures. If toxicity is suspected the infusion will be stopped per the standard of care at University Hospital.

Routine evaluation and management for those undergoing robot assisted laparoscopic prostatectomy include:

- ASA classification, assigned by the anesthesiologist
- Deep venous thrombosis prophylaxis per standardized pathway
- Estimated blood loss
- Use of intraoperative fluids (crystalloid, colloid, blood products)

Routine evaluation and management for those undergoing robot assisted laparoscopic partial nephrectomy, these include:

- ASA classification, assigned by the anesthesiologist
- Deep venous thrombosis prophylaxis per standardized pathway
- Duration of warm ischemia time
- Estimated blood loss
- Use of intraoperative fluids (crystalloid, colloid, blood products)

TOXICITIES/SIDE EFFECTS

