Length of hospital stay will be defined as the time the subject leaves the OR until subject meets standardized discharge criteria according to the surgeons' protocol, which will exclude social factors delaying real discharge times.

Post-operative ileus duration is defined as return of bowel function in hours from extubation per patients recall following nursing inquiry. Documentation will be done per standard of care by the nurse caring for study patient.

Flatus return is defined as return of flatus in hours from extubation per patients recall following nursing inquiry. Documentation will be done by nurse caring for patient following standard of care.

Patient satisfaction will be assessed 24 hours post-operative by Post Anesthesia Patient Satisfaction Assessment by research staff.

CRITERIA FOR REMOVAL FROM STUDY

Patients will be withdrawn from the study if they express a desire to do so, if it is determined to be in the patient's best interest to do so, or if they do not undergo initiation of their surgical procedure as stipulated previously. If lidocaine infusion is stopped subject will be excluded from analysis. If surgery is converted from robotic assisted to open the subject will be excluded from analysis. Patients who are not evaluable for the study primary endpoint by failure to obtain

data for the primary endpoint will be excluded from the study and further analysis will not be performed.

BIOSTATISTICS

Sample Size

The primary outcome for the study is the patient's pain score at discharge. Although additional analyses are planned, the sample size estimate is based on this outcome. Assuming a common standard deviation of two-points, a sample size of 40 with 20 per treatment arm will provide 80% power to detect a 2-point difference between groups when testing a two-sided alternative at the 5% level of significance using Wilcoxon Rank Sum Test. To take into account the loss to follow up, the drop-out inflated enrollment will be 46 subject with 23 subjects in each group assuming the same power.

Unadjusted and Adjusted Analysis

The unadjusted analysis will be designated as primary analysis and it will be performed to assess the pain level difference between the two groups. The adjusted analysis which will be designated as secondary analysis will incorporate other covariates like type of surgery in addition to the treatment assignments as covariate.

Proposed Analyses

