Two statistical analysis methods will be used to make a comparison between the two treatment groups with regard to the primary end point: (i) to assess the difference of pain level between the two groups at specific time point, Wilcoxon Rank Sum Test will be used, (ii) to assess the pattern of change in pain level over the study period between the two groups, a Generalized Estimation Equation (GEE) model will be used.

Sample Size					Drop-out Inflated Enrollment	
Treatment	Placebo	Effect Size	SD	Power	Treatment	Placebo
20	20	2	2	80%	23	23
27	27	2	2	90%	30	30

*A dropout rate of 10% was considered here. A Two Sample T-test using effect size sample size method was used to get an estimate of the samples needed from the PASS program.

Table 2: Sample size assuming 80% and 90% power.

RESEARCH PARTICIPANT REGISTRATION AND RANDOMIZATION PROCEDURES

Research Participant Registration

Confirm eligibility as defined in the section entitled Criteria for Patient/Subject Eligibility.

Obtain informed consent, by following procedures defined in section entitled Informed Consent Procedures.

Randomization

Randomization will be accomplished by the method of random permuted block and stratified by the type of the surgery and subject age. Since this is a double-blind study, the subjects' treatment assignments will be kept in a blinded randomization table. The Excel column containing treatment designation assigned by a biostatistician will be occluded from view to maintain blinding. The investigational pharmacist will not be blinded and will have the randomization table. After recruitment, research staff will randomize the patient into the correct stratification and the Investigation Pharmacy will be notified. If it is clinically necessary to unblind a subjects' treatment allocation this will be done using the randomization table.

DATA MANAGEMENT ISSUES

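### Randomisation is stratified by surgery type and age, but the primary Wilcoxon test uses neither factor and no analysis names age; adjusting for both would be a free gain in power if they predict pain.

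*Combined protocol and SAP*

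**What the plan says.** The sections that bear on this point are:

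- **Randomization:** "Randomization will be accomplished by the method of random permuted block and stratified by the type of the surgery and subject age". No age cut-point is given.
- **Overview of Study Designation, Design:** "Patients will be randomized in a 1:1 fashion and stratified by the type of surgery to receive" the infusion. Age is not mentioned as a stratification factor.
- **Surgical Intervention Plan:** "the randomization will be additionally stratified by the type of the surgery". Again age is not mentioned.
- **Biostatistics, Sample Size:** "The primary outcome for the study is the patient's pain score at discharge".
- **Biostatistics, Unadjusted and Adjusted Analysis:** the main comparison takes no covariates: "The unadjusted analysis will be designated as primary analysis and it will be performed to assess the pain level difference between the two groups". Covariates enter only in a secondary analysis, which "will incorporate other covariates like type of surgery in addition to the treatment assignments as covariate".
- **Biostatistics, Proposed Analyses:** groups are compared at a given time point by the Wilcoxon rank sum test, with no strata. For the pattern over time, "a Generalized Estimation Equation (GEE) model will be used", with no covariates listed.

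No reason is given for leaving the stratification factors out of the primary test.

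**The concern.** Stratified blocks force the arms to be nearly balanced on surgery type and age. The treatment comparison is then more precise than under simple randomisation, if those factors are related to pain. The ordinary Wilcoxon test does not know about the balance. It leaves the between-stratum variation in its error term, overstates the variance of the comparison and rejects too rarely.

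The stake is efficiency, not validity. With 40 evaluable patients, the trial would balance on two factors and then not use them. A secondary matter is that the adjusted analysis has an open covariate list, so whether age enters it could be settled after the data are seen.

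**Working it through.** **1. The plan's own sample size.** Inputs from Sample Size and Table 2: difference 2, SD 2 (standardised effect 2/2 = 1), two-sided 5%, dropout 10%.

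- A two-sample t-test at 80% power needs 16.7, so 17 per arm. Dividing by 0.864, the minimum relative efficiency of the Wilcoxon test, gives 17/0.864 = 19.7, so 20 per arm. For 90% power, 23/0.864 = 26.6, so 27.
- Dropout: 20/0.9 = 22.2, so 23; 27/0.9 = 30.

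Both rows of Table 2 reproduce. The factor 0.864 is inferred from that match; the documents do not state it. With normal data and 20 per arm the Wilcoxon test has about 85–86% power, so the design has some reserve over 80%.

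**2. Why the unadjusted test is conservative.** Let R² be the share of pain variance explained by the two factors. With exact balance within strata, the true variance of the comparison is about (1 − R²) times what the unadjusted test assumes. Its true two-sided size is then roughly 2[1 − Φ(1.96/√(1 − R²))]:

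- R² = 0.1: 1.96/0.949 = 2.07, size 3.9%
- R² = 0.2: 1.96/0.894 = 2.19, size 2.8%
- R² = 0.3: 1.96/0.837 = 2.34, size 1.9%

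**3. What R² means in points.** Assume R² is split equally between the factors, with 50% of patients aged 65 or over and 35% having nephrectomy (shares not in the documents). Each factor then explains a variance of 4 × R²/2, which equals p(1 − p) × gap². For R² = 0.1:

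- age gap = √(0.2/0.25) = 0.89 points
- surgery gap = √(0.2/0.2275) = 0.94 points

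**4. Simulation.** 40 patients, blocks of 4 (assumed) within four strata, total SD 2, 8,000 runs per setting. Rank ANCOVA means a linear model on the overall ranks with treatment, surgery type and age group.

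| R² (assumed) | Gap by age / surgery (points) | Size, Wilcoxon | Size, rank ANCOVA | Power at 2 points, Wilcoxon | Power at 2 points, rank ANCOVA | Gain (points) |
|---|---|---|---|---|---|---|
| 0 | 0 / 0 | 4.9% | 5.2% | 85.6% | 85.7% | 0.1 |
| 0.05 | 0.63 / 0.66 | 4.7% | 5.3% | 85.7% | 86.6% | 0.9 |
| 0.1 | 0.89 / 0.94 | 3.9% | 5.1% | 85.4% | 87.8% | 2.4 |
| 0.2 | 1.26 / 1.33 | 3.0% | 4.6% | 86.8% | 91.4% | 4.6 |
| 0.3 | 1.55 / 1.62 | 2.1% | 5.0% | 87.9% | 94.2% | 6.3 |

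The simulation standard error is about √(0.05 × 0.95/8000) = 0.24 percentage points for size and √(0.86 × 0.14/8000) = 0.39 for power. The simulated sizes agree with the approximation in step 2.

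**5. Sensitivity to the assumptions.**

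- *Other stratum shares (35% aged 65 or over with 50% nephrectomy; 65% with 20%), and whole-number scores limited to 0–10:* at R² = 0.1, 0.2 and 0.3 the Wilcoxon size is 4.0–4.4%, 3.1–3.7% and 2.2–2.6%, and the gain is 2.0–2.7, 4.2–4.9 and 5.6–6.9 points. At R² = 0 the gain is 0–0.2 points.
- *46 randomised, 40 analysed, so that dropout breaks some blocks:* at R² = 0, 0.1, 0.2 and 0.3 power is 84.7, 84.1, 86.2 and 87.0% unadjusted against 84.7, 86.8, 90.7 and 93.8% for the rank ANCOVA.
- *True difference of 1.5 points:* unadjusted power is only about 60%, and the rank ANCOVA gains about 1, 4, 9 and 14 points at R² = 0, 0.1, 0.2 and 0.3.
- *Stratified Wilcoxon (van Elteren) instead of rank ANCOVA:* at R² = 0 it has 82.6% power against 85.7% unadjusted, because some strata are small. It overtakes the unadjusted test only above R² of about 0.1.

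**The case against.** The strongest reply is that nothing in the plan is wrong. A pre-specified unadjusted test with an adjusted secondary analysis is a legitimate choice. Its false-positive rate is protected and its power exceeds 80% under the plan's assumptions. Its power does not fall as R² rises; the loss exists only relative to a better test. All of this stands, and it limits the weight of the point.

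The benefit also depends on an R² that the documents do not give. Gains of 5 to 6 points need gaps of roughly 1.3 to 1.6 points for each factor, against a planned treatment effect of 2. The Surgical Intervention Plan does refer to physiologic differences, but only to say that "impact from physiologic differences between the 2 approaches are expected to be equally distributed between the 2 arms". That is a statement about balance and does not show that surgery type predicts pain. So the larger gains are possible but not shown to be likely.

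The covariate wording gives surgery type as an example, so age is not excluded. The plan uses 65 as its age threshold for the infusion rate, so the intended cut-point can be guessed. Both are true, but neither commits the analysis in advance.

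Finally, adjustment is not free for every method: the van Elteren test loses about 3 points when the factors do not matter. The rank ANCOVA shows no such loss. Its treatment term is in rank units, however, while the trial is planned in points, so an estimate in points should accompany it.

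**Conclusion.** The concern holds as an efficiency point; it does not make the planned test invalid. If surgery type and age explain 10–30% of the variance in discharge pain, the nominal 5% test runs at about 3.9% to 2.1%. It then has about 2 to 6 points less power at a 2-point difference than a rank ANCOVA on both factors. If they explain 5% or less, the difference is 1 point or less. These figures assume SD 2, blocks of 4 and the stratum shares above, and they changed little when the shares and score scale were varied.

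That age is a stratification factor rests on the Randomization section alone, so the mismatch with the other two sections needs correcting whatever is decided about the test. The change is recommended rather than essential.

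**What to change.** 1. Make the primary test of discharge pain a rank ANCOVA: rank the scores over all patients, fit a linear model on the ranks with treatment, surgery type and age group (<65/≥65), and test the treatment term two-sided at 5%.
2. Report with it an adjusted mean difference in points with a 95% confidence interval, from a linear model on the raw scores with the same factors.
3. Keep the unadjusted Wilcoxon test as a sensitivity analysis.
4. Name surgery type and age group in the adjusted analysis and in the GEE model, and close the covariate list.
5. Make the Design, Surgical Intervention Plan and Randomization sections agree on the stratification factors, and state the age cut-point used for randomisation. If it is not 65, use the actual cut-point in item 1.

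If the unadjusted test stays primary, the plan should say why, and items 4 and 5 still apply.

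The cost is wording, provided it is settled before unblinding. Both factors are known at randomisation, so no data or patients are added. The model spends two degrees of freedom, and simulated power when the factors explain nothing is unchanged (85.7% against 85.6%).

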Anesthesia will be maintained with 1 MAC sevoflurane, additional fentanyl and rocuronium will be given per anesthesia discretion. Quantity of all anesthetic and analgesic medications during the operation will be documented. Local 0.25% bupivacaine (10mL) without epinephrine injection will be used post-operatively during closure in all patients regardless of being in the study group or control group as a part of normal operational procedure. Reversal of neuromuscular blockade will be with sugammadex 2 mg/kg. When standard extubation criteria are met the subject will be extubated and transported to PACU.

Intervention

Fifteen minutes following endotracheal intubation, subjects will be intravenously infused with either 0.8% lidocaine at 1 mg/kg/h if < age 65 and 0.5 mg/kg/h if ≥ age 65 or an equal volume and rate of normal saline placebo as determined by the randomization table. The infusion will be continued for 24 hours after surgery. Masked infusion bags of 0.8% lidocaine or normal saline will be prepared by the Investigational Pharmacy at the University of Missouri Hospital according to the subject randomization table. Infusion preparation will occur in a blinded fashion to all clinical and research personal involved with the study case. To maintain blinding, the investigational pharmacist will enter "Study Medication" in the medical record.

In PACU patient will receive additional fentanyl or hydromorphone. Postoperative pain scores, vital measures, and opioid use will be documented. Once patient is able to tolerate oral intake, they will be switched to oral narcotics. Patient fentanyl consumption and 10 cm visual analog scale (VAS) will be utilized. VAS will be scored from a 0 "no pain" to a 10 "worst pain ever" and will be recorded by blinded research staff at 1, 2, 4, 6, 12, 24 hours post-operatively, postop day 2, any additional day during hospitalization, at time of discharge and 14-day follow up. The nurse that will be caring for these patients will document the time of first bowel movement, return of flatus and any adverse reactions per standard of care. Post-Anesthesia Patient Satisfaction Assessment will be performed at 24 h post-surgery.

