Surgical complications will be assessed prospectively and retrospectively and reviewed using the institutional standard for complications reporting for all surgical patients as followed by the Department of Surgery. Standardized graded complications and adverse effects at UM utilize the five-point modified Clavien-Dindo system. Grade I include complications requiring monitoring but no intervention; Grade II requires bedside or medical treatment; Grade III constitute adverse events requiring surgical or procedural intervention with return to normal functioning; Grade IV includes disabling, life-threatening complications with resulting functional loss and grade V is death of the patient. This is a modification of the Clavien-Dindo system for reporting complications with defined, categorized and classified events that will be segregated into time periods of ≤ 30 days, 31-90 days and > 90 days after surgery and includes medication complications following NCI CTCAE version 5 guidelines.

CRITERIA FOR THERAPEUTIC RESPONSE/OUTCOME ASSESSMENT

If the surgery is aborted for any reason before attempted excision of the mass or intravenous infusion fails for any reason, the patient will be removed from the study and replaced. Based on past experience these issues are rare events. If a partial nephrectomy converts to radical nephrectomy, infusion will be continued and the data will be collected. If any robotic procedure converts to an open procedure, the subject will be excluded from the study. Lidocaine infusion will be continued or started (if subject is receiving normal saline) per surgeon request.

The intraoperative period is defined as the period from anesthesia induction to the extubation of the trachea. The surgical time is determined from the incision to the final skin closure.

The postoperative period is defined as the period from the extubation to the study endpoint at 14 days \pm 7 days.

Blood loss is defined as the estimate accounted from the suction device and absorptive sponges during the procedure, as described and agreed upon by the surgeon, anesthesiologist, circulating nurse, and surgical technician as covered by institutional guidelines.

Post-operative pain will be defined by the patient through the use of a 10 cm visual analog scale (VAS) and 11 point numeric scale (0-10).

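### The GEE for the course of pain has no small-sample correction at about 20 patients per arm; with categorical time and an uncorrected Wald chi-square test, its type I error would be about 12–15% (6–7 times) or 17–20% (8–9 times)

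*Combined protocol and SAP*

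**What the plan says.** The Sample Size section names as primary outcome the "pain score at discharge. Although additional analyses are planned, the sample size estimate is based on this outcome". It plans "a sample size of 40 with 20 per treatment arm", "testing a two-sided alternative at the 5% level of significance using Wilcoxon Rank Sum Test". Table 2 raises enrolment to 23 per arm for 10% dropout.

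Proposed Analyses then gives two methods for comparing the arms on the primary endpoint. The first is the Wilcoxon test at a specific time. The second concerns the "pattern of change in pain level over the study period between the two groups, a Generalized Estimation Equation (GEE) model will be used". The only other text that bears on the model is in Unadjusted and Adjusted Analysis: "The unadjusted analysis will be designated as primary analysis", with an adjusted secondary analysis that brings in covariates such as surgery type.

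The Intervention section has VAS scores "recorded by blinded research staff at 1, 2, 4, 6, 12, 24 hours post-operatively", then on postoperative day 2, on any further hospital day, at discharge and at the 14-day follow-up. The outcome section defines the postoperative period as "the period from the extubation to the study endpoint at 14 days", with a window of 7 days either side. Randomization is "stratified by the type of the surgery and subject age".

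The document does not state which of these times enter the GEE, how time is coded, which term is tested, or which variance estimator and reference distribution apply.

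**The concern.** The sandwich variance of a GEE is justified by a large number of independent subjects. With about 40 it is biased downward. In addition, a chi-square reference ignores the uncertainty in the estimated covariance matrix. Both faults grow with the number of parameters tested together. A group-by-time test with categorical time has one degree of freedom fewer than the number of times, so a rich pain schedule in a small trial is the unfavourable case.

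The claim at stake is that pain follows a different course under lidocaine than under placebo. Since the GEE is listed under the primary endpoint, a small p-value from it would probably be reported next to the discharge result.

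**Working it through.** **1. The plan's own figure.** Inputs from the Sample Size section are a difference of 2, SD 2, two-sided 5%, and 80% or 90% power. An exact two-sample t-test needs 17 or 23 per arm. Dividing by 0.864, the minimum asymptotic efficiency of the Wilcoxon test relative to the t-test, gives 17/0.864 = 19.7 and 23/0.864 = 26.6, hence 20 and 27. Dividing by 0.9 for dropout gives 22.2 and 30, hence 23 and 30. This matches Table 2. The plan states no error rate for the GEE.

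**2. Candidate time sets (assumed, because the plan does not choose).**
- 6 times: 1, 2, 4, 6, 12 and 24 h
- 7 times: adding the 14-day visit
- 8 times: adding discharge
- 9 times: adding postoperative day 2

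**3. Formula.** Let n be patients per arm, p the number of times minus 1, and ν = 2n − 2. In a saturated group-by-time model with complete data, the GEE estimates are the cell means, whatever the working correlation. The uncorrected sandwich divides by n where the unbiased covariance divides by n − 1. The Wald statistic is therefore W = T² × n/(n − 1), with T² Hotelling's statistic. For normal data, T² × (ν − p + 1)/(νp) follows F(p, ν − p + 1). Hence

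type I error = P{ F(p, ν − p + 1) > χ²(p; 0.95) × [(n − 1)/n] × (ν − p + 1)/(νp) }.

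Example with n = 20 and 6 times: p = 5, ν = 38, χ² = 11.07. The threshold is 11.07 × 0.95 × 34/190 = 1.882, and P{F(5, 34) > 1.882} = 12.3%. The correct 5% threshold is 2.494.

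**4. Results for a nominal 5% group-by-time test.** The Kauermann-Carroll correction multiplies the variance by n/(n − 1), so W = T².

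| Times (p) | Uncorrected, χ², n = 20 | Uncorrected, χ², n = 23 | Kauermann-Carroll, χ², n = 20 | Kauermann-Carroll, scaled F |
|---|---|---|---|---|
| 6 (5) | 12.3% | 11.2% | 10.7% | 5.0% |
| 7 (6) | 14.5% | 12.9% | 12.5% | 5.0% |
| 8 (7) | 16.9% | 14.9% | 14.6% | 5.0% |
| 9 (8) | 19.7% | 17.1% | 17.1% | 5.0% |

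Correcting the sandwich but keeping chi-square removes little of the excess; the reference distribution matters more.

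**5. Milder readings at n = 20.** A one-degree-of-freedom uncorrected Wald test, such as a linear slope, gives 6.4%. The score statistic W/(1 + W/2n), with the uncorrected W, gives 4.3% (6 times) and 4.0% (7 times).

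**6. Size on the p-value scale, n = 20.** The true 5% point of T² is 13.93 (6 times) or 16.51 (7 times), against chi-square values of 11.07 and 12.59. Multiplied by 20/19 and read on the chi-square scale, these mean that a printed p would have to fall below 0.012 or 0.008 for a true 5% level.

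**7. Simulation checks.**
- Scores rounded and bounded at 0–10, exchangeable or AR(1) correlation 0.5, 10,000 runs, n = 20: 12.7–12.8% (6 times) and 14.5–14.6% (7 times) uncorrected; 5.0–5.6% with Kauermann-Carroll and the scaled F.
- Fitted exchangeable GEE, 1,000 runs, n = 20, complete data: 11.0%, 15.3%, 16.5% and 17.8% uncorrected for 6 to 9 times; 3.5–4.5% with a bias-reduced sandwich and an F reference.
- Exchangeable GEE, 7 times, 1,500 runs, n = 20: 14.9% uncorrected and 5.5% with the proposed test when 10% of scores are missing at random; 15.5% and 5.7% with surgery type and age group in the model.

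**The case against.** The strongest reply is that the inflation is not a property of the plan. It needs four choices together, none of them written down: categorical time, a joint group-by-time test, an uncorrected sandwich and a chi-square reference. A slope or a score test is equally compatible with the text and is close to 5%. This stands, and it is why the error rates above are conditional. A reader might infer that the planned GEE has a 12–20% false-positive rate. The documents do not support that, because they do not select the test that produces it.

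A reader might also infer that the trial's main result is compromised. It is not: the sample size rests on the Wilcoxon test of discharge pain, which is untouched, and no decision rule is tied to the GEE p-value.

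The number of times is also open to dispute. Discharge pain is scheduled for every patient and is the sizing outcome, so leaving it out of the count needs a reason. There is one: it has no fixed clock time and may coincide with another score. Day 2 may be obtained only from patients still in hospital. Because the plan settles neither matter, both ranges are given.

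The objection does not remove the point. Any uncorrected Wald version is anti-conservative at this size, slightly for a slope and badly for categorical time, and nothing in the plan prevents the version being chosen after the data are seen.

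**Conclusion.** The point holds in conditional form and should be addressed. At about 20 patients per arm, the permitted versions of this GEE run from about 4% to nearly 20% true error at a nominal 5%. Under the uncorrected Wald chi-square test with categorical time, between 1 null trial in 8 (6 times, 12.3%) and 1 in 5 (9 times, 19.7%) would show a false difference in the course of pain, instead of 1 in 20. At 23 per arm the range is 11.2% to 17.1%.

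The closed form assumes normal scores, complete data and equal arms. Simulation with bounded scores, missing data and covariates gives similar figures. The time sets are an assumption. Confidence is medium, because the plan does not say which test would be run.

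**What to change.** Keep the Wilcoxon test for discharge pain. For the GEE, prespecify:

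- **Time:** categorical nominal times at 1, 2, 4, 6, 12 and 24 h and the 14-day visit, noting that visit's window.
- **Working correlation:** one named structure, for example exchangeable.
- **Test:** one test of group by time, using the Kauermann-Carroll bias-corrected sandwich and F = W(ν − p + 1)/(νp) on p and ν − p + 1 degrees of freedom, with ν = patients minus 2 and p = number of times minus 1.
- **Discharge score:** state that it is analysed by the Wilcoxon test and left out of the nominal-time model, for the reasons given above.
- **Day 2:** include it only if it is collected from every patient. Otherwise report it and later inpatient days descriptively, with the number still in hospital in each arm.
- **Covariates:** keep the unadjusted model primary, and add both randomisation strata (surgery type and age group) to the adjusted secondary model.

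The cost is a few sentences of analysis text. Intervals at each time become about 6% wider at 20 per arm, (2.024/1.96) × √(20/19) = 1.06, and about 5% wider at 23 per arm, (2.015/1.96) × √(23/22) = 1.05. P-values for the longitudinal analysis will be larger than from the uncorrected test, and the scaled F may need a short hand calculation if the software does not provide it.
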